7.5.3 Subsequent Therapy

Subsequent therapy will be summarized and listed.

- Subsequent Therapy
 - Systemic anti-cancer therapy by drug name
 - Surgery

– Radiotherapy

A by-subject listing of follow-up therapy will be produced for subjects who had any subsequent therapy.

7.5.4 *Interim Analyses*

Cohorts A1 and B1: No interim analysis for futility is planned, as the Cohorts are expected to be fully enrolled when the OS endpoint becomes available. However, in Module A if other indications are stopped for futility, enrollment in Module B may be initiated based on recommendations of the Steering Committee.

Cohorts A2 and B2: The interim futility analysis for Cohorts A2 and B2 (HGG) will be conducted using PFS(6) and after at least 8 participants have been followed for 6 months. In addition, all other available efficacy data will be evaluated in the futility analysis.

Cohorts A3 and B3: An interim analysis based on PFS(6) for futility only will be conducted after at least 8 of the planned number of participants are enrolled with 6 months follow-up. In addition all other available efficacy data will be evaluated in the futility analysis.

Cohorts A4 and B4: No interim analysis for futility is planned as the sample size is too small.

Cohorts A5 and B5: No interim analysis for futility is planned as it is comprised of many diverse histologies. However, in Module A if other indications are stopped for futility enrollment in Module B may be initiated based on the recommendation of the Steering Committee.

Cohort 4 has a smaller sample size than the other cohorts (n=10) so it is not appropriate to add an interim analysis for futility.

For Cohorts 2 and 3: The Bayesian statistical methodology is described in Bayesian Adaptive Methods for Clinical Trial by Berry et al published in Chapman and Hall (2011) and is outlined here with adaptations from [REDACTED] [REDACTED].

- 1) Once 8 subjects have been followed for at least 6 months a Cox proportional hazards model will be fit to interim data and estimate of hazard rate obtained.
- 2) Based on memoryless property of exponential survival times will be generated for each subject conditional on the observed data using the estimated hazard rate and one-sample log rank test applied to the fully enrolled cohort. The simulated trial will be declared success if log rank is significant.
- 3) Simulations will be repeated 1000 times. The predictive probability of success is defined as the proportion of simulated trials that are declared success based on observed interim data.
- 4) If predictive probability of success is <20%, futility may be declared. The totality of data will be considered in any decision to stop the cohort.

7.5.5 *Final Analysis*

The final analysis (study closure analysis) will be conducted once the last subject was followed for 100 days post treatment dose and 36-month survival follow up from study entry has been

conducted for each subject where applicable. The study will be closed after the final analyses, which include but not limited to updated safety analyses and OS, are completed.

7.6 Safety

Primary safety analyses will be performed for safety lead-in participants which includes 3 groups: in Module A, the first 14 DLT-evaluable participants in Cohort 1, and the first 10 DLT-evaluable participants in Cohorts 2-5; in Module B, the first 10 DLT-evaluable participants.

Secondary safety analyses will be performed for all treated subjects and summarized by cohort and treatment.

7.6.1 Deaths

See Core Safety SAP¹.

7.6.2 Serious Adverse Events

See Core Safety SAP¹.

7.6.3 Adverse Events Leading to Discontinuation of Study Therapy

See Core Safety SAP¹.

7.6.4 Adverse Events Leading to Dose Delay of Study Therapy

See Core Safety SAP¹.

7.6.5 Adverse Events

See Core Safety SAP¹.

7.6.6 Select Adverse Events

See Core Safety SAP¹.

7.6.7 Immune-Mediated Adverse Events

The immune-mediated adverse events (IMAE) consist of a list of preferred terms grouped by specific category (e.g. pneumonitis, diarrhea/colitis, see Core Safety SAP for select adverse events). The IMAE categories and terms are defined by the Sponsor and the list that is the most current at the time of analysis will be used. This list will be based on the most current version of MedDRA at the time when integrated database will be built. The final list will be included as appendix in CSR.

Table 7.6.7-1: Immune-Mediated Adverse Events

Class Name of IMAE	PT TERM	Order in the output
PNEUMONITIS	PNEUMONITIS Interstitial lung disease	1
DIARRHEA/COLITIS	COLITIS DIARRHEA ENTEROCOLITIS	2
HEPATITIS	HEPATOTOXICITY HEPATITIS HEPATITIS ACUTE AUTOIMMUNE HEPATITIS ASPARTATE AMINOTRANSFERASE INCREASED ALANINE AMINOTRANSFERASE INCREASED BLOOD BILIRUBIN INCREASED HYPERBILIRUBINAEMIA BLOOD ALKALINE PHOSPHATASE INCREASED	3
ADRENAL INSUFFICIENCY	ADRENAL INSUFFICIENCY	4
HYPOTHYROIDISM/THYROIDITIS	HYPOTHYROIDISM THYROIDITIS ACUTE AUTOIMMUNE THYROIDITIS THYROIDITIS	5
HYPOTHYROIDISM	HYPOTHYROIDISM	6
THYROIDITIS	AUTOIMMUNE THYROIDITIS THYROIDITIS THYROIDITIS ACUTE	7
HYPERTHYROIDISM	HYPERTHYROIDISM	12
HYPOPHYSITIS	HYPOPHYSITIS	13
DIABETES MELLITUS	DIABETES MELLITUS DIABETIC KETOACIDOSIS	8
NEPHRITIS AND RENAL DYSFUNCTION	NEPHRITIS NEPHRITIS ALLERGIC TUBULOINTERSTITIAL NEPHRITIS RENAL FAILURE ACUTE RENAL FAILURE BLOOD CREATININE INCREASED	9
RASH	RASH Rash maculo-papular	10

Table 7.6.7-1: Immune-Mediated Adverse Events		
Class Name of IMAE	PT TERM	Order in the output
HYPERSENSITIVITY	HYPERSENSITIVITY INFUSION RELATED REACTION	11
OTHER	Myasthenic Syndrome Myasthenia Gravis Myasthenia Gravis Crisis Myasthenic Syndrome Demyelination Event Demyelination Guillain-Barre Syndrome Guillain-Barre Syndrome Miller Fisher Syndrome Pancreatitis Event Autoimmune Pancreatitis Pancreatitis Pancreatitis Acute Pancreatitis Necrotising Uveitis Event Chorioretinitis Cyclitis Intermediate uveitis Iridocyclitis Iritis Uveitis	14

All summaries in the following subsections for IMAEs based on extended follow-up (100 day window after the last dose).

7.6.7.1 Incidence of IMAEs

Immune-Mediated AEs by worst CTC grade (both classifications, that are, “Any Grade, Grade 3-4, Grade 5” and “Worst CTC Grade”, unless noted otherwise) will be summarized by Category/PT for each category:

- Summary of any endocrine IMAE
- Summary of IMAE where immune modulating medication was initiated
- Summary of IMAEs [only by Worst CTC Grade]
- Summary of endocrine serious IMAEs
- Summary of serious IMAEs where immune modulating medication was initiated
- Summary of any endocrine IMAEs leading to dose delay or reduction
- Summary of IMAEs leading to dose delay or reduction where immune modulating medication was initiated
- Summary of endocrine IMAEs leading to discontinuation
- Summary of IMAEs leading to discontinuation where immune modulating medication was initiated

7.6.7.2 Management of IMAEs

Following summaries will be presented

- Summary of duration of immune modulating concomitant medication for IMAE management
- Summary of immune modulating concomitant medication for IMAE management
- Summary of immune modulating concomitant medication for Grade 3 to 5 IMAEs management

7.6.7.3 Time to Onset and Resolution of IMAEs

Time to onset and resolution for IMAEs will be analyzed. Following summaries will be presented

- Summary of time to onset of endocrine IMAE
- Summary of time to onset of IMAEs where immune modulating medication was initiated
- Summary of time to resolution of endocrine IMAEs
- Summary of time to resolution of endocrine IMAEs where immune modulating medication was initiated

7.6.7.4 Re-Challenge

Subjects who had infusion of nivolumab after the onset of IMAE were considered re-challenged subjects. Following summary will be presented for re-challenged subjects.

- Summary of subjects who were re-challenged with nivolumab by IMAE category

Listings of IMAEs will also be provided

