7.4.1 Dose Delay Criteria

Premedications are not recommended for the first dose of nivolumab.

Participants should be carefully monitored for infusion reactions during nivolumab administration. If an acute infusion reaction is noted, participants should be managed according to [Section 9.2.9](#).

Doses of nivolumab and ipilimumab may be interrupted, delayed, or discontinued depending on how well the participant tolerates the treatment. Dosing visits are not skipped, only delayed. Tumor assessments for all participants should continue as per protocol even if dosing is delayed. During Module B (nivolumab and ipilimumab combination), both nivolumab and ipilimumab should be delayed at the same time. There will be no dose escalations or reductions of nivolumab allowed.

For the purposes of this trial, a fixed ULN = 45 will be used for AST and ALT.

Nivolumab administration should be delayed for the following:

- Grade 2 non-skin, drug-related adverse event, with the exception of fatigue
- Grade 2 drug-related creatinine, AST, ALT and/or Total Bilirubin abnormalities
- Grade 3 skin, drug-related adverse event

- Grade 3 drug-related laboratory abnormality, with the following exceptions:
 - Grade 3 lymphopenia or asymptomatic amylase or lipase does not require dose delay
 - Grade ≥ 3 AST, ALT, Total Bilirubin will require dose discontinuation (see [Section 9.2.7](#))
- Any AE, laboratory abnormality, or intercurrent illness which, in the judgment of the investigator, warrants delaying the dose of study medication.

Participants who require delay of nivolumab should be re-evaluated weekly or more frequently if clinically indicated and resume nivolumab dosing when re-treatment criteria are met.

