All participants who discontinue study treatment should comply with protocol specified follow-up procedures as outlined in [Section 2](#). The only exception to this requirement is when a participant withdraws consent for all study procedures including post-treatment study follow-up or loses the ability to consent freely (ie, is imprisoned or involuntarily incarcerated for the treatment of either a psychiatric or physical illness).

If study treatment is discontinued prior to the participant's completion of the study, the reason for the discontinuation must be documented in the participant's medical records and reported page.

8.1.1 *Discontinuation of Nivolumab Due to Toxicity [Module A or B]*

For the purposes of this trial, a fixed ULN = 45 will be used for AST and ALT.

Nivolumab treatment should be permanently discontinued for the following:

- Any Grade 2 drug-related uveitis, eye pain or blurred vision that does not respond to topical therapy and does not improve to Grade 1 severity within the re-treatment period OR requires systemic treatment

- Any Grade 3 non-skin, drug-related adverse event lasting > 7 days or recurs, with the following exceptions for laboratory abnormalities, drug-related uveitis, pneumonitis, bronchospasm, neurologic toxicity, hypersensitivity reactions, infusion reactions, and endocrinopathies:
 - Grade 3 drug-related uveitis, pneumonitis, bronchospasm, neurologic toxicity, hypersensitivity reaction, myocarditis or infusion reaction of any duration requires discontinuation
 - Grade 3 drug-related endocrinopathies, adequately controlled with only physiologic hormone replacement do not require discontinuation. Adrenal insufficiency requires discontinuation regardless of control with hormone replacement.
 - Grade 3 drug-related laboratory abnormalities do not require treatment discontinuation except:
 - ◆ Grade 3 drug-related thrombocytopenia > 7 days or associated with bleeding requires discontinuation
 - ◆ Grade ≥ 3 drug-related AST, ALT or Total Bilirubin requires discontinuation*
 - ◆ Concurrent AST or ALT > 3 x ULN and total bilirubin > 2x ULN (see [Section 9.2.7](#))
- Any Grade 4 drug-related adverse event or laboratory abnormality (including but not limited to creatinine, AST, ALT, or Total Bilirubin), except for the following events which do not require discontinuation:
 - Grade 4 neutropenia ≤ 7 days
 - Grade 4 lymphopenia or leukopenia or asymptomatic amylase or lipase

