7.4.2 Modifications of Study Therapy

7.4.2.1 Dose Delays

For nivolumab, treatment may be delayed for up to a maximum of 6 weeks from the last dose. Subjects receiving nivolumab may be dosed no less than 12 days from the previous dose.

Each study medication infusion may be delayed independently. A dose will be considered as actually delayed if the delay is exceeding 3 days (i.e., greater than or equal to 4 days from scheduled dosing date) from previous dose for any given study medication. The length of delay for nivolumab is defined as (duration of previous cycle in days - 14). The length of delay for ipilimumab is defined as (duration of previous cycle in days - 42). Dose delays for each study medication will be divided into following categories: on-time, 4 - 7 days, 8 - 14 days, 15 - 42, > 42 days. Reason for dose delay will be retrieved from the respective CRF dosing pages for each study medication. If different reasons for delay are recorded (in the same cycle), both the reasons will be reported.

The following parameters will be summarized by cohort and treatment group.

- Number of subjects with at least one dose delayed, number of dose delayed per subject, Length of Delay and Reason for Dose Delay

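### SAP 7.6.7.4 counts any nivolumab infusion after IMAE onset as re-challenge, so it does not separate children held and restarted from children dosed on schedule through a mild event

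*SAP*

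**What the plan says.** SAP 7.6.7.4 gives one rule: "Subjects who had infusion of nivolumab after the onset of IMAE were considered re-challenged subjects". One table rests on it, "Summary of subjects who were re-challenged with nivolumab by IMAE category", together with listings of IMAEs. The section does not refer to the Core Safety SAP.

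SAP 7.6.7 defines the events: "The immune-mediated adverse events (IMAE) consist of a list of preferred terms grouped by specific category". Table 7.6.7-1 includes rash, diarrhea, hypothyroidism, raised AST and ALT, and infusion related reaction. No grade threshold is stated.

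Protocol 7.4.1 lists when nivolumab is to be delayed. The general entry for non-skin events is "Grade 2 non-skin, drug-related adverse event, with the exception of fatigue"; the entry for skin events is at Grade 3. The investigator may also delay a dose on judgment. Protocol 7.4.2 then sets separate criteria for resuming after a delay.

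On data, SAP 7.4.2.1 says: "Reason for dose delay will be retrieved from the respective CRF dosing pages for each study medication".

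**The concern.** In ordinary use, re-challenge means giving a drug again after it was stopped or held for an event. The SAP rule needs no stop or hold, so two different experiences share one line: continuing through an event that never called for a delay, and restarting after an event that did.

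The table is the only planned output on re-challenge. It is likely to be read as evidence on restarting nivolumab after an immune-mediated event in children with CNS tumours. Children who were never interrupted can only add to that count. SAP 7.6.7.4 also lists no summary of whether the event came back, which is what a reader of such a table would want next.

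**Working it through.** The plan gives no figure to reproduce. The check is whether the documents allow uninterrupted dosing after IMAE onset, and whether anything narrows the rule.

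1. **The rule (SAP 7.6.7.4).** A subject counts if there is an infusion of nivolumab after onset. There is no condition on hold, delay, grade, resolution or recurrence.

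2. **The events (SAP 7.6.7).** Listed preferred terms qualify at any grade, so Grade 1 events and Grade 2 rash are included.

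3. **The delay criteria (Protocol 7.4.1).** A Grade 1 non-skin event and a Grade 1-2 skin event meet none of the listed triggers, investigator judgment aside.

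4. **The dosing interval (Protocol 7.1.1 and 7.1.2).** Module A doses every 2 weeks. Module B doses every 3 weeks for 4 doses, then every 2 weeks. For a child who stays on schedule, the next infusion is due within about 14 or 21 days of onset.

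5. **Together.** A child with a Grade 1 thyroid event or a Grade 2 rash can receive the next dose on time and be reported as re-challenged.

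6. **Infusion reactions (Protocol 7.4.3).** Grade 1 reactions are handled without interruption, and Grade 2 reactions by interrupting the infusion. Both carry a recommendation of premedication at later infusions; the section does not delay the next dose. That next infusion is a real re-exposure, but not a restart after a hold.

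7. **Other outputs.** SAP 7.6.7.1 plans summaries of IMAEs leading to dose delay or reduction, but these do not show who was dosed again afterwards.

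**Size.** Let C be the children dosed without interruption and H those held and restarted. The SAP reports C + H; restarts are H; the overstatement is C. The documents give neither number. As an assumption only, take 10 children with an IMAE, of whom 3 stop for good, so that C + H = 7 and the SAP reports 7 of 10:

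| Assumed C | Assumed H | SAP count | Restarted after a hold |
|---|---|---|---|
| 0 | 7 | 7 of 10 | 7 of 10 |
| 4 | 3 | 7 of 10 | 3 of 10 |
| 7 | 0 | 7 of 10 | 0 of 10 |

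The same reported count fits every row.

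**Can the delay derivation be reused to split the count?** Not as written. SAP 7.4.2.1 takes nivolumab delay as the previous cycle's length minus 14 days. An on-time 3-week Module B cycle gives 21 − 14 = 7 days, above the SAP's 3-day threshold, so it would score as delayed. The CRF reason for delay does not have this problem.

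**The case against.** The strongest reply is that 7.6.7.4 should be read with its neighbours. In SAP 7.6.7.1 most summaries are limited either to endocrine events ("Summary of any endocrine IMAE") or to treated events ("Summary of IMAE where immune modulating medication was initiated"), and 7.6.7.3 follows the same pattern. If that restriction carries over, many mild events drop out. This would shrink the problem but not remove it: 7.6.7.4 does not state the restriction, endocrine events need no such medication to be counted, and starting a medication is not the same as holding a dose.

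Second, the rule is stated openly, and the dose-delay summaries, the by-subject dosing listing and the IMAE listings should let a determined reader sort held from continued subjects. That is fair, but no planned table does it.

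Third, the sponsor may want the same count across its programme; SAP 7.6.10 gives programme consistency as its reason for another choice. That is a good reason to keep the existing count, not to label it re-challenge.

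Fourth, a rule based only on delayed doses would put re-exposure after an infusion reaction under uninterrupted dosing. This stands, and those events need their own line. It also stands that the SAP shows a delay reason is collected, but not that it is linked to a particular adverse event.

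**Conclusion.** The definition does not separate re-challenge from continued dosing, and the table can overstate experience with restarting. The amount cannot be derived from the documents. This rests on reading 7.6.7.4 as written, without a restriction borrowed from 7.6.7.1 or from the Core Safety SAP, which is not among the documents. It is a minor point: one descriptive safety table, with no effect on an efficacy endpoint, error rate or sample size.

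Three stronger readings are tempting and are not supported:

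- *The table does not describe re-challenge at all.* Children held and restarted do have an infusion after onset and are counted; they are just not identifiable.
- *Nearly every child who stays on treatment is counted, so the table is mostly uninterrupted dosing.* Children who stay on treatment include true restarts, and the share never held is unknown. Grade 2 non-skin drug-related events call for a delay, which may keep that share small.
- *Hormone-replaced endocrinopathies are dosed through.* Protocol 8.1.1 says only that "Grade 3 drug-related endocrinopathies, adequately controlled with only physiologic hormone replacement do not require discontinuation"; it is silent on delay. Protocol 7.4.2 places endocrinopathies controlled by hormone replacement under resuming treatment, which for those children is a hold followed by a restart. The point rests instead on Grade 1 non-skin and Grade 1-2 skin events.

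**What to change.** In SAP 7.6.7.4, relabel the existing count *any nivolumab infusion after IMAE onset* and split it by IMAE category:

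- (a) infusion after a dose was delayed or withheld because of that IMAE, identified from the CRF reason for delay and not from the cycle-length-minus-14-days formula;
- (b) dosing without interruption for that IMAE;
- (c) re-exposure after an infusion-related or hypersensitivity reaction, on its own line.

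Report recurrence of the same IMAE category in (a) and (c). State whether the table covers all listed IMAEs or only endocrine and medicated events as in 7.6.7.1. Footnote any child whose delay reason cannot be matched to an event.

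The cost is a little extra derivation, mainly matching the delay reason to the IMAE, which may need manual review if the CRF does not link the two. Comparison with programme tables is kept because the present count stays. Nothing changes in treatment or in the collection of delay reasons.

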7.6.8 Immune Modulating Medication

See Core Safety SAP¹.

7.6.9 Multiple Events

See Core Safety SAP¹.

7.6.10 Clinical Laboratory Evaluations

The analysis population for each laboratory test is restricted to treated subjects who underwent that laboratory test. ALT and AST ULN provided by the external vendor will be used rather than the protocol specified fixed ULN of 45 for clinical laboratory toxicity grading for consistency across Nivo program.

7.6.10.1 Hematology

See Core Safety SAP¹.

7.6.10.2 Serum Chemistry

See Core Safety SAP¹.

[figure not shown]

[figure not shown]
7.6.12 Vital Signs

See Core Safety SAP¹.

7.7 Pregnancy

See Core Safety SAP¹.

8 CONVENTIONS

The following conventions may be used for imputing partial dates for analyses requiring dates:

For missing and partial adverse event onset dates, imputation will be performed using the Adverse Event Domain Requirements Specification¹². Missing and partial Non-Study Medication Domain dates will be imputed using the derivation algorithm described in 4.3.3 of BMS Non-Study Medication Domain Requirements Specification¹³.

For death dates, the following conventions will be used for imputing partial dates:

- If only the day of the month is missing, the 1st of the month will be used to replace the missing day. The imputed date will be compared to the last known date alive day and the maximum will be considered as the death date.
- If the month or the year is missing, the death date will be imputed as the last known date alive day
- If the date is completely missing but the reason for death is present the death date will be imputed as the last known date alive day

For date of progression, the following conventions will be used for imputing partial dates:

[figure not shown]
- If only the day of the month is missing, the 1st of the month will be used to replace the missing day*.
- If the day and month are missing or a date is completely missing, it will be considered as missing.

*In cases where the date of death is present and complete, the imputed progression date will be compared to the date of death. The minimum of the imputed progression date and date of death will be considered as the date of progression.

For other partial/missing dates, the following conventions may be used:

- If only the day of the month is missing, the 15th of the month will be used to replace the missing day.
- If both the day and the month are missing, “July 1” will be used to replace the missing information.
- If a date is completely missing, it will be considered as missing.

The following conversion factors will be used to convert days to months or years: 1 month = 30.4375 days and 1 year = 365.25 days.

All statistical analyses will be carried out using SAS (Statistical Analysis System software, SAS Institute, North Carolina, USA) unless otherwise noted.

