8.3 Lost to Follow-Up

- All reasonable efforts must be made to locate participants to determine and report their ongoing status. This includes follow-up with persons authorized by the participant.
- Lost to follow-up is defined by the inability to reach the participant after a minimum of **three** documented phone calls, faxes, or emails as well as lack of response by participant to one registered mail letter. All attempts should be documented in the participant's medical records.
- If it is determined that the participant has died, the site will use permissible local methods to obtain date and cause of death.
- If investigator's use of third-party representative to assist in the follow-up portion of the study has been included in the participant's informed consent, then the investigator may use a Sponsor retained third-party representative to assist site staff with obtaining participant's contact information or other public vital status data necessary to complete the follow-up portion of the study.
- The site staff and representative will consult publicly available sources, such as public health registries and databases, in order to obtain updated contact information.
- If after all attempts, the participant remains lost to follow-up, then the last known alive date as determined by the investigator should be reported and documented in the participant's medical records.

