4.1.2 Expansion Phase

4.1.2.1 Overall Survival for Cohort 1

The primary endpoint of Cohort 1 is overall survival (OS). OS for Cohort 1 is defined as the time between the date of diagnosis and the date of death in Cohort 1. A participant who has not died will be censored at the last known alive date. OS will be followed continuously while participants are on study drug and every 3 months via in-person or phone contact during the survival follow-up phase of the study drug.

4.1.2.2 Progression Free Survival for Cohorts 2 to 5

The primary endpoints of Cohort 2-5 are progression-free survival (PFS).

PFS is defined as the time from first dose to the date of the first documented tumor progression or death due to any cause. Participants who die without a reported prior progression will be considered to have progressed on the date of death. Participants who did not have disease progression or die will be censored at the date of last evaluable tumor assessment. Participants who did not have any on study tumor assessment and did not die will be censored at the first dose date. PFS will be determined by investigators based on RANO criteria. First tumor assessments will occur at week 6 and 12, and will be at every 8 weeks for the first year and then every 12 weeks thereafter until disease progression is documented.

Table 4.1.2.2-1: Censoring Scheme used in Analysis of PFS

Situation	Date of Progression or Censoring	Outcome
No baseline tumor assessments	First dose date	Censored
No on study tumor assessments and no death	First dose date	Censored
Documented progression	Date of the first documented progression per RANO	Progressed
Diagnostic surgical resection without documented progression prior or on the same day and without confirmed disease progression from tumor pathology	Date of last tumor assessment prior to initiation of the diagnostic surgical resection	Censored
No progression and no death	Date of last assessment for disease progression	Censored
Subsequent therapies, including new anticancer therapy, tumor-directed radiotherapy, or tumor-directed surgery received, without progression reported prior or on the same day	Date of last assessment for disease progression prior to initiation of the subsequent therapy	Censored
Death without progression	Date of death	Progressed

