7.5.1 Overall Survival

7.5.1.1 Overall Survival for Cohort 1

As the primary efficacy endpoint of Cohort 1, the OS is defined as the time between the date of diagnosis and the date of death. A participant who has not died will be censored at the last known alive date.

The OS curves for each treatment group will be estimated using the Kaplan-Meier (KM) product-limit method. Median OS and the corresponding two-sided 80% confidence intervals using the log-log transformation will be computed.

The distribution of OS will also be compared against the historical control of an exponential distribution with median OS 9 months [REDACTED] using a one-sided one-sample log rank test when approximately 17 events have occurred or after each participant has been followed for at least 24 months.

As one of the secondary endpoints, survival rate at 12 months will be estimated using KM estimates on the OS curve and its corresponding 95% confidence interval will be derived based on Greenwood formula.

7.5.1.2 Overall Survival for Cohorts 2 to 4

As the secondary efficacy endpoints of cohorts 2 to 4, the OS is defined as the time between the first dose date and the date of death. A participant who has not died will be censored at the last known alive date.

The OS curves for each treatment group will be estimated using the Kaplan-Meier (KM) product-limit method. Median OS and the corresponding two-sided 95% confidence intervals using the log-log transformation will be computed.

Survival rate at 12 month will be estimated using KM estimates on the OS curve and its corresponding 95% confidence interval will be derived based on Greenwood formula.

7.5.1.3 Overall Survival for Cohort 5

OS will be listed. OS curve will be computed using Kaplan-Meier method for pooled indications and selected individual indications. The corresponding 95% confidence interval for median OS will be calculated via Brookmeyer and Crowley methodology using log-log transformation.

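### A death recorded with a year but no month is dated at last known alive, which can contradict the recorded year; rare and conservative, but a one-line correction

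*SAP*

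**What the plan says.** SAP section 8 opens by saying that its conventions may be applied, but the wording for deaths is firm: "For death dates, the following conventions will be used for imputing partial dates". Three cases follow.

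- Only the day missing: the 1st of the recorded month is taken, and then "The imputed date will be compared to the last known date alive day and the maximum will be considered as the death date".
- Month or year missing: "If the month or the year is missing, the death date will be imputed as the last known date alive day".
- Whole date missing, but a reason for death given: last known alive again.

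For dates other than death and progression, the same section keeps a recorded year: "If both the day and the month are missing, “July 1” will be used to replace the missing information". A progression date with only a year is treated as missing.

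The death date feeds the Cohort 1 primary endpoint, since "OS for Cohort 1 is defined as the time between the date of diagnosis and the date of death in Cohort 1" (SAP 4.1.2.1; SAP 7.5.1.1 agrees). It also sets PFS for a child who dies without recorded progression (SAP 4.1.2.2). Survival contacts are planned every 3 months, within 14 days either way (Protocol Table 2.-4, footnote b). For a child lost to follow-up, Protocol 8.3 says: "If it is determined that the participant has died, the site will use permissible local methods to obtain date and cause of death".

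**The concern.** The second case covers dates that are partly known but treats them like dates of which nothing is known. The day-missing rule takes the earliest date that fits the record and never goes before last contact. The month-missing rule drops the first half of that logic. When the recorded death year is later than the year of last contact, the imputed date must contradict the record, and no other part of either document adds a check against the year.

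The affected quantities are the Cohort 1 test of OS against a 9-month median (22 children, about 17 deaths), median OS, OS(12) where the date crosses 12 months, and PFS where death is the event.

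**Working it through.** **1. The plan's Cohort 1 figure.** Inputs from SAP section 5 and the Protocol synopsis: medians 9 and 15 months, exponential, 12 months' accrual, 24 months' follow-up, one-sided alpha 10%, power 80%, N = 22, 17 events.

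- Monthly hazards: ln2/9 = 0.0770 and ln2/15 = 0.0462; ratio 9/15 = 0.6.
- Probability that a death is observed under the target, with uniform accrual: 1 − (1/12)∫₀¹² exp(−0.0462(24+u)) du = 0.747.
- Events = (1.2816 + 0.8416)² / (ln 0.6)² = 17.3; N = 17.3/0.747 = 23.1.
- Using the exact variance under the target gives N = 23.7 with 17.7 events. Two simpler variance forms give 18.8 and 18.1.
- Simulated power at N = 22 is 79.6%, with 22 × 0.747 = 16.4 expected deaths. The plan's 22, 17 and 80% are reproduced closely enough and are not in dispute.

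**2. The date rule applied.** The dates are assumed examples, each with death recorded as 2019, month unknown. Conversion: "1 month = 30.4375 days and 1 year = 365.25 days".

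| Last known alive | SAP death date | Earliest date that fits the record | Least understatement |
|---|---|---|---|
| 10 Feb 2019 | 10 Feb 2019 | 10 Feb 2019 | 0 |
| 15 Nov 2018 | 15 Nov 2018 | 1 Jan 2019 | 47 days = 1.5 months |
| 10 Oct 2018 | 10 Oct 2018 | 1 Jan 2019 | 83 days = 2.7 months |
| 10 Mar 2018 | 10 Mar 2018 | 1 Jan 2019 | 297 days = 9.8 months |

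In the last row the child's expected deaths under the null fall by at least 9.76 × ln2/9 = 0.75.

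**3. Bound when contacts are kept.** The longest gap is 3 + 14/30.4375 = 3.5 months if one contact is at the edge of its window, and 3 + 28/30.4375 = 3.9 months if two neighbouring contacts are at opposite edges. The last row of the table therefore needs several missed contacts.

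**4. Effect on the Cohort 1 test.** Z = (O − E)/√E, with benefit declared if Z < −1.2816. Shortening one death by s months lowers E by s × 0.0770, so 3 months gives 0.23. There were 40,000 simulated trials per setting, at N = 22. The number of deaths affected is an assumption.

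| Deaths dated early | Months early | Power | Type I error |
|---|---|---|---|
| 0 | – | 79.6% | 8.3% |
| 1 | 1.5 | 79.0% | 8.0% |
| 1 | 3 | 78.7% | 7.8% |
| 1 | 3.9 | 77.8% | 7.6% |
| 2 | 3 | 77.4% | 7.1% |
| 2 | 12 (extreme) | 72.8% | 5.2% |

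A second simulation (60,000 trials per setting) gave 79.8% with correct dates, and 78.6% and 77.5% with one or two deaths 3 months early.

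These losses are measured against true death dates. The fix below recovers only the part up to 1 January.

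**The case against.** The strongest reply is that the case hardly arises. It needs an unknown month, a recorded year, and a year later than that of last contact. OS is followed continuously on drug and every 3 months afterwards, the sponsor may ask for extra survival sweeps, and SAEs, which include deaths, are collected to 100 days after the last dose. Nothing in the documents suggests that year-only deaths are expected. This stands, and it limits the weight of the point.

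The error is also conservative. It shortens OS against a historical control, so type I error falls. This stands too, but the stated objective is to estimate OS, and a cautious test does not justify a date that the record contradicts.

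July 1, which the SAP uses elsewhere, is another possible choice. That is an argument about which replacement to use and does not defend the present rule.

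A reader might go further in two ways that the documents do not support.

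- *That Protocol 8.3 relies on public vital-status sources, so year-only deaths are likely.* In that section, staff consult public sources to update contact details. Retrieval of vital status by a third party is optional and depends on the consent given. That such sources would return only a year is an assumption.
- *That a large loss of power is to be expected.* With one, two or three deaths dated 10 months early, simulated power falls to 77.1%, 73.8% and 70.7%. Three such deaths would be 3/17 = 18% of the planned events, each after a long loss of contact. These are extremes measured against true dates, so they overstate both the likely harm and what the fix would recover.

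**Conclusion.** The point holds as a minor correction. The month-missing rule can place a death in a calendar year that the record shows the child survived, and it does so whenever the recorded death year is later than the year of last contact. The provable error is at most about 3.5 to 3.9 months if survival contacts are kept, and larger only after loss to follow-up. One Cohort 1 death dated 3 months early costs about 1 point of power (about 80% to 79%).

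The power figures assume exponential survival, the planned accrual and follow-up, and a chosen number of affected deaths, which the documents do not give. The direction is against the treatment, so a reader should not infer that the rule could produce a false claim of benefit in the OS test.

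**What to change.** Replace the second death-date bullet in SAP section 8 with: *If the month is missing but the year is known, January 1 of that year is compared with the last known alive date and the maximum is the death date; if the year is missing, the last known alive date is used.*

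This is the SAP's own day-missing logic one level up. It removes the contradiction, never dates a death before last contact, and still uses the earliest date that fits the record. It recovers only the time from last contact to 1 January.

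There is one small downside. The PFS censoring table (SAP Table 4.1.2.2-1) has no rule for missed assessments. For a child lost to follow-up without recorded progression, and not censored for subsequent therapy, the later death date would also lengthen PFS by unobserved time. List every child whose death date is imputed from the year alone, with the last contact and last tumour assessment dates.

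The cost is one line of SAP wording, the matching programming and a short listing. No new data are needed.
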